9.4.4 SAFETY ANALYSES

We will inquire about AE's at each visit as described above in the Safety and Other Assessment section above (section 8.2). AE's will initially be inquired about by clinical research coordinators and may then be assessed by study physicians during the same visit. The study physician in charge of assessing a given AE will provide a thorough description of the event in the participant's CRF and the AE will be followed up at each visit (or more frequently if needed) until it has completely resolved or until 30 days from the participant's last study visit. The study physician will specifically report on start date, stop date, severity, relationship, expectedness, outcome, and duration, as well as whether or not the AE meets criteria for a SAE. AE's will be coded based upon Medical Dictionary for Regulatory Activities (MedDRA) criteria, coded only once per participant (e.g. should a participant have a headache at each visit only a single headache AE will be coded), and compiled continuously for DSMB and progress reports. AE's will specifically be presented in table format based on System Organ Class, and grouped based on severity, relationship, and expectedness. Adverse events leading to premature discontinuation from the study intervention and serious intervention-emergent AE's, should they occur, will be presented separately in regulatory reports and final publications in table format. Once data lock and unblinding has occurred, safety data will be compared between active and sham aiTBS using chi-squared tests (or Fisher's exact test if indicated).

9.4.5 BASELINE DESCRIPTIVE STATISTICS

Demographic data will be summarized for sham and active intervention groups separately using standard descriptive statistics. For continuous measures (i.e. age and years of education), means and standard deviations will be calculated, and any group differences will be identified using univariate ANOVAs. Categorical measures (i.e. sex and race/ethnicity) will be quantified by counts and percentages, and any group differences will be detected using Chi-squared tests. Characteristics that display imbalance at the baseline measure or an association with the dependent variable will be assessed for inclusion as covariates in the final models.

9.4.6 PLANNED INTERIM ANALYSES

Because of the anticipated low level of adverse events of aiTBS given our recently completed smaller RCT, interim analysis of data, protocol and adverse events is not anticipated to be necessary. Serious adverse events will be reviewed on a monthly basis, unless a more urgent review is requested. As described in section 7, only under extreme circumstances or if it were determined that a high level of side effects was

due to aiTBS, would the PD be charged with breaking the study mask. This study will be stopped prior to its completion if: [1] the intervention is associated with adverse effects that call into question the safety of the intervention; [2] difficulty in study recruitment or retention will significantly impact the ability to evaluate the study endpoints; [3] any new information becomes available during the study that necessitates stopping the study; or [4] other situations occur that might warrant stopping the study.

9.4.7 SUB-GROUP ANALYSES

We are recruiting 100 participants of all gender, ethnic, and racial backgrounds. We will assess the role of gender in our analyses to determine the potential utility of additional follow-up projects that focus on any discovered gender-based observations. However, it may not be feasible to run sub-group analyses in this study because of potentially insufficient sub-group sample sizes.

9.4.8 TABULATION OF INDIVIDUAL PARTICIPANT DATA

All participant data will be directly exported from REDCap. The exported data will be listed in a long format, such that each row (i.e. observation) represents a specific time point for each subject. The individual variables collected will be represented by columns (i.e. measures). For reproducibility, data will be exported and tabulated using either the R or Python programming language.

9.4.9 EXPLORATORY ANALYSES

Two additional analyses will be applied to exploring the intervention effect-related FC features in the whole brain: the brain networks' organization and the multivariate FC patterns.

The brain is thought to organize in the way that brain regions could work together to maximize the ability to respond to cognitive demands while minimizing the wiring cost. Accordingly, brain regions are found to be closely correlated within brain networks, but for the regions across brain networks the correlations are relatively weaker or even anti-correlated²¹³. We will calculate brain network segregation²¹⁴ to explore the relationship between the organization of brain networks and intervention effect. We will use Power's parcellation²¹⁵ and extract data from: somatosensory-motor, default-mode, frontoparietal, ventral attention, dorsal attention, cinguloopercular and salience networks. In order to calculate the brain network segregation, the mean within network correlation (R_{within}) will be calculated by averaging the FCs for regions within each network, and the mean between network ($R_{between}$) correlation will be calculated by averaging the FCs for regions from two different networks. Only positive correlations will be used in these calculations. And then the brain network segregation (BNS) will be calculated as: $(R_{within} - R_{between}) / R_{within}$ ²¹⁶. BNS will then be compared between baseline and post-intervention to find the intervention related BNS, and then the group differences will also be tested. Linear regression models will be used to test the relationship between BNS and both depression scores and acute mood states.

We also will use TDA-based Mapper analysis (Saggar et al 2018; 2022) to investigate how brain state transitions (at rest) evolve in patients with depression undergoing accelerated iTBS intervention. By constructing high-dimensional manifolds of neuroimaging data and visualizing their topological structures as graphs, we aim to identify patterns of brain state changes associated with treatment. Additionally, we

will characterize the dose-response relationship of iTBS by analyzing how dosage (over the course of treatment) influences these state transitions, providing insights into individualized treatment optimization.

To understand the physiological mechanisms underlying the stimulation effects, we will employ the reduced Wong-Wang (RWW) neural mass model to simulate whole-brain dynamics. This modeling approach will complement our empirical analyses by providing mechanistic insights into how aiTBS influences brain network dynamics. The RWW model will be implemented by modeling each brain region as a neural mass unit described by the RWW equations. Structural connectivity data from diffusion MRI will inform the coupling between regions, and model parameters will be calibrated using resting-state fMRI data from baseline measurements. Stimulation effects will be modeled as external input to the targeted regions, with both direct stimulation effects and network-wide propagation being simulated. statistical analysis of model outputs will be compared with empirical fMRI data using Pearson correlation between simulated and observed functional connectivity patterns, root mean square error between model predictions and actual measurements, and analysis of dynamic functional connectivity states and their temporal evolution. For parameter optimization, we will employ Bayesian optimization to identify model parameters that best reproduce the observed changes in sgACC-DMN connectivity, network-wide reorganization patterns, and individual variation in treatment response. This approach will allow us to systematically explore the parameter space while accounting for the complex interactions between different model components. A crucial component of our analysis will focus on evaluating changes in model parameters, particularly the excitation/inhibition (E/I) balance across brain regions. We will quantify how aiTBS modulates the E/I balance by analyzing changes in local coupling parameters and synaptic gains before and after intervention. Statistical comparisons of these parameters between active and sham conditions will be performed using mixed-effects models with appropriate corrections for multiple comparisons. Additionally, we will examine the relationship between E/I balance changes and clinical outcomes to identify potential biomarkers of treatment response.

This modeling framework will provide insights into the causal chain from stimulation to observed clinical effects, individual variation in treatment response, and optimal stimulation parameters for maximizing therapeutic impact. The analysis will integrate with our primary and secondary endpoints by providing mechanistic explanations for observed changes in functional connectivity and clinical outcomes, while offering a deeper understanding of how aiTBS modulates neural dynamics through changes in local circuit properties and E/I balance.

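### Section 9.4.9 fits the E/I parameters to treatment response and then tests them against clinical outcome in the same participants, with no out-of-sample step

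*Combined protocol and SAP*

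**What the plan says.** Section 9.4.9 (Exploratory Analyses) adds a whole-brain neural mass model to the empirical imaging analyses. The steps that matter here are these.

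- Calibration: "model parameters will be calibrated using resting-state fMRI data from baseline measurements".
- Stimulation: "Stimulation effects will be modeled as external input to the targeted regions". The section does not say whether this input is switched on by arm.
- Optimisation: Bayesian optimisation is used to "identify model parameters that best reproduce the observed changes in sgACC-DMN connectivity, network-wide reorganization patterns, and individual variation in treatment response".
- Quantity analysed: E/I balance change is obtained by "analyzing changes in local coupling parameters and synaptic gains before and after intervention".
- Test against arm: "Statistical comparisons of these parameters between active and sham conditions will be performed using mixed-effects models with appropriate corrections for multiple comparisons".
- Test against outcome: the investigators will "examine the relationship between E/I balance changes and clinical outcomes to identify potential biomarkers of treatment response".
- Use of the result: it is to be integrated with the primary and secondary endpoints by "providing mechanistic explanations for observed changes in functional connectivity and clinical outcomes".

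The section gives no objective function and no weights for the three optimisation targets. It does not say whether fitting is per participant. It describes no hold-out sample, cross-validation or permutation, and no blinding of the fit to arm or clinical scores.

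**The concern.** A parameter tuned to reproduce a variable will tend to correlate with that variable in the data used for tuning, whether or not a real link exists. Here response is listed as a fitting target, and the fitted parameter is then examined as a biomarker of response in the same people. The correction for multiple comparisons deals with the number of tests, not with this reuse of data. Baseline calibration is not a hold-out either, because the later optimisation uses post-baseline change and response.

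What is at stake is interpretation. This is a mechanistic trial, and the modelling is offered as an explanation of the primary and secondary findings. Readers would take an E/I-outcome association as corroboration, although it could be a by-product of the fit.

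**Working it through.** The plan states no figure for this analysis, so there is none to reproduce. The check is an illustration of how the test behaves when there is no true E/I-outcome link.

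**Inputs from the plan.** Two-sided alpha is 0.05 (section 9.4.1). Section 9.2 requires 40 per arm, recruits 50 and expects about 25% loss: 50 × 0.75 = 37.5. Sample sizes of 37, 40 and 50 per arm were therefore used.

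**Assumptions.** T is the true E/I change, F the connectivity change and Y the clinical outcome. They are independent within arm, each with variance 1. The fitted parameter is θ = (1 − w)·g + w·Y, with g = √0.5·T + √0.5·F. The weight w of clinical response is taken from 0 to 0.5. Both the weights and the linear form are assumed.

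**Outcome test (correlation of θ with Y, adjusted for arm).** The implied correlation is r = w / √((1 − w)² + w²). By the Fisher z approximation with 80 participants and one covariate, the rejection rate is about Φ(atanh(r)·√76 − 1.96), plus a small opposite tail.

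Example, w = 0.2: r = 0.2 / √(0.64 + 0.04) = 0.243; atanh(r)·√76 = 0.2475 × 8.72 = 2.16; Φ(2.16 − 1.96) = Φ(0.20) = 58%.

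Simulated false-positive rates (10,000 trials per setting):

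| w | r | 37 per arm | 40 per arm | 50 per arm |
|---|---|---|---|---|
| 0 | 0 | 4.6% | 4.8% | 5.0% |
| 0.1 | 0.110 | 15% | 16% | 19% |
| 0.2 | 0.243 | 56% | 58% | 68% |
| 0.3 | 0.394 | 94% | 95% | 98% |
| 0.5 | 0.707 | 100% | 100% | 100% |

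With response removed from the fit (w = 0), the test returns to its nominal level.

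**Arm test (t-test on θ, 40 per arm).** For a standardised arm difference δ in θ, the rejection rate is about Φ(δ·√20 − 1.96), plus a small opposite tail.

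- No arm difference in F or Y: simulated 4.6% to 5.0% at every w.
- F differs by d = 1, true E/I does not, w = 0: δ = √0.5 = 0.707; 0.707 × 4.47 = 3.16; Φ(1.20) = 88%. Simulated 88%.
- Y differs by d = 1, true E/I does not: simulated 8%, 18%, 41% and 88% at w = 0.1, 0.2, 0.3 and 0.5.
- Stimulation input coded by arm, with an assumed shift in θ of 0.3 or 0.5 and no arm effect on F, Y or T: 0.3 × 4.47 = 1.34 and 0.5 × 4.47 = 2.24, giving Φ(−0.62) = 27% and Φ(0.28) = 61%. Simulated 26% and 61%.

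**The case against.** The strongest reply concerns the meaning of treatment response. A neural mass model simulates brain activity, and every measure of fit listed in section 9.4.9 is an imaging measure: correlation of simulated with observed connectivity, root mean square error, and dynamic connectivity states. Neither MADRS-S nor IMS-12 is named as a fitting target. The closing paragraph of the section lists clinical effects and individual variation in response as separate items. On this reading no symptom score enters the fit, and the outcome test is not circular in the way described. The section also does not say that the optimised parameters are exactly those later analysed as E/I balance.

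This shows that the clinical reading is not certain. It remains the natural one: connectivity change and network reorganisation are already the first two targets, so a third target confined to imaging would be largely redundant, and the sentence on biomarkers ties the same term to clinical outcomes. If imaging response was meant, the plan should say so. The E/I-outcome association would then largely re-express secondary endpoint (a), the relation between connectivity change and MADRS-S change, and would add little independent evidence.

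It can also be said that fitting a mechanistic model to the phenomenon it explains is the purpose of such modelling, that the plan speaks only of potential biomarkers, and that E/I balance is absent from the objectives and endpoints in section 3. All of this stands, and it keeps the severity low.

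**Conclusion.** On the natural reading the E/I-outcome test is circular as written, and its false-positive rate exceeds 5%. The size of the excess cannot be determined, because it depends on the unstated weight given to response. The rates above rest on an assumed linear form and assumed weights; they show direction and plausible range, not a prediction.

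Three stronger readings are not supported. A reader might infer that a positive active-versus-sham difference is built in. Arm is not a fitting target, and that test holds about 5% when neither connectivity nor symptoms differ by arm. It does stop being independent evidence when they differ, or if the stimulation input is coded by arm. A reader might derive an error rate from the number of parameter settings the optimiser tries, but the plan describes no step that keeps the setting best correlated with response. Finally, nothing here affects the decision rules in sections 9.4.2 and 9.4.3. This is a low-severity point about an exploratory analysis.

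**What to change.** In section 9.4.9:

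- State the objective function, and remove clinical response from it.
- Fit each scan to imaging data only, blind to arm and clinical scores.
- Use the same stimulation coding in both arms, or justify coding it by arm.
- If clinical response is kept as a target, test the E/I-outcome link only out of sample (nested cross-validation) or by a permutation test that repeats the whole fit and test with clinical scores shuffled among participants.
- Report model fit on data not used for fitting.
- Describe any E/I difference that follows from the connectivity difference as a model-based restatement, not as independent support for the primary and secondary endpoints. This is needed even after the other changes, because a fit to each scan's connectivity still carries the sgACC-DMN change.

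The cost is wording and computing time, and a less favourable reported model fit. No new data or visits are needed.

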10. SUPPORTING DOCUMENTATION AND OPERATIONAL CONSIDERATIONS

10.1 REGULATORY, ETHICAL, AND STUDY OVERSIGHT CONSIDERATIONS

10.1.1 INFORMED CONSENT PROCESS

10.1.1.1 CONSENT/ASSENT AND OTHER INFORMATIONAL DOCUMENTS PROVIDED TO PARTICIPANTS

Consent forms describing in detail the study intervention, study procedures, and risks are given to the participant and written documentation of informed consent is required prior to starting intervention/administering study intervention. The following consent materials are submitted with this protocol:

Two signed consent forms will be obtained from each participant: (1) Screening consent form and (2) Study consent form. These consent forms will be administered electronically using Adobe Sign.

10.1.1.2 CONSENT PROCEDURES AND DOCUMENTATION

Informed consent is a process that is initiated prior to the individual agreeing to participate in the study and continues throughout the individual's study participation. Consent forms will be IRB-approved and the participant will be asked to read and review the document. The study investigator or his designee will explain the research study to the participant and answer any questions that may arise in a private setting. A verbal explanation will be provided in English of the purposes, procedures, and potential risks of the study and of their rights as research participants. Participants will have the opportunity to carefully review the written consent form and ask questions prior to signing. The participant will sign the informed consent document prior to any procedures being done specifically for the study. Participants will be informed that participation is voluntary and that they may withdraw from the study at any time, without prejudice. A copy of the informed consent document will be given to the participants for their records. The informed consent process will be conducted and documented in the source document (including the date), and the form signed, before the participant undergoes any study-specific procedures. The rights and welfare of the participants will be protected by emphasizing to them that the quality of their medical care will not be adversely affected if they decline to participate in this study.

Consenting Processes: There will be two consent forms: one consent for screening procedures, and the other for study and enrollment procedures. For the first consent process, the clinical research coordinator (CRC) will screen the participant's eligibility for enrollment in the study. The study PD or psychiatrist or their designee will consent the participants for the second phase of the consenting process, which involves discussing the risks of the rTMS procedure and MRI scanning. The participant will be consented in the sequence that has been defined by our protocol.

Education and Informed Consent Process: Consent forms will be Institutional Review Board (IRB)-approved, and the participant will be asked to read and review the document. The participant will sign the informed consent document prior to any procedures being done specifically for the study. The signature will be electronically obtained as described above. The consent process will start with an introductory paragraph that describes the study. This statement will be followed by a description of the purpose of the research. The participant will be informed that this is a double blind study and they have a 50% chance of receiving active stimulation and that their participation is voluntary. Next, the duration of study involvement and the procedures involved will be described.

The participant will be notified of the discomforts and risks along with the potential benefits. The participant will receive a *Statement of Confidentiality*. The participant will be notified as to the costs for participation (none) as well as the compensation for participation. The participant will be made aware of the research funding source. The participant will be given information regarding the fact that their participation is voluntary. The rights and welfare of the participants will be protected by emphasizing to

them that the quality of their medical care will not be adversely affected if they decline to participate in this study. The participant will be made aware of their alternative options. The participant will then be given the contact information for questions or concerns. The participant will have the opportunity to carefully review the written consent form and ask questions prior to signing. The participants will have the opportunity to discuss the study with their family or surrogates or think about it prior to agreeing to participate. The participant will sign the informed consent document prior to any procedures being done specifically for the study. All participants will be provided a copy of their signed consent forms.

Finally, after reading the experimental subjects' bill of rights, the participant will be asked for their signature in order to consent and give permission to be in the research study. To ensure the participant has capacity to consent, as part of this process the study psychiatrist or their designee will complete a Capacity to Consent form.

Plan for Review of Consent Document: The signed consent document will be confirmed by the PD, study psychiatrist, or their designee (which includes regulatory staff).

Documentation of Signed Consent: The screening and enrollment logs will be utilized to record the consent and screening of all subjects and the outcome of each screening. These logs will provide a comprehensive list of all subjects who were screened for eligibility and all participants who enrolled into the study. This information will be maintained in REDCap. All subjects who were consented and screened on site will be included in these logs, including screen failures.

10.1.2 STUDY DISCONTINUATION AND CLOSURE

This study may be temporarily suspended or prematurely terminated if there is sufficient reasonable cause. Written notification, documenting the reason for study suspension or termination, will be provided by the suspending or terminating party to study participants, investigator, and funding agency. If the study is prematurely terminated or suspended, the Protocol Director (PD) will promptly inform study participants, the Institutional Review Board (IRB), and sponsor and will provide the reason(s) for the termination or suspension. Study participants will be contacted, as applicable, and be informed of changes to study visit schedule.

Circumstances that may warrant termination or suspension include, but are not limited to:

- Determination of unexpected, significant, or unacceptable risk to participants
- Insufficient compliance to protocol requirements
- Data that are not sufficiently complete and/or evaluable

Study may resume once concerns about safety, protocol compliance, and data quality are addressed, and satisfy the sponsor, IRB and/or Food and Drug Administration (FDA).

